**Plan for statistical analysis of efficacy and safety parameters**

of a patient or subject of a clinical trial to whom a medicinal (investigational) product has been administered, regardless of the causal relationship with its use.

An adverse event may be any unfavourable and unintended change (including a deviation of a laboratory indicator from the norm), symptom or disease, the time of occurrence of which does not exclude a causal relationship with the use of the medicinal product, regardless of the presence or absence of a relationship with the use of the medicinal product.

If any adverse events develop, the investigator should complete the relevant pages of the patient's CRF, assess the appropriateness of the patient's continued participation in the trial. Adverse events will be recorded from the time the first dose of the investigational product is administered to the patient in the trial until completion of the trial.

The severity of AEs is assessed as follows:

The investigator assesses the severity of an adverse event according to the Common Terminology Criteria for Adverse Events (CTCAE) current version at the time of the trial. If an adverse event cannot be classified according to the CTCAE criteria, the investigator will choose the closest description of the severity of the adverse event from those given in the classification based on personal clinical experience:

Degree of severity	Category	Definition/Description
1	Mild	No symptoms or mild symptoms, only clinical or diagnostic follow-up is required; no intervention is indicated
2	Moderate	Only minimal, localised or non-invasive interventions are indicated; limitation of daily living activities
3	Severe	Severe or clinically significant but not immediately life-threatening; hospitalization or prolongation of hospitalization indicated; disability; limitation of self-care in activities of daily living
4	Life-threatening/ Disability to work	Life-threatening consequences, urgent intervention required
5	Fatal	Death associated with an adverse event

"Severe" adverse event will not necessarily be "serious" in nature, "serious" adverse event will not necessarily be "severe" by definition.

The association of an AE with the use of investigational products will be assessed using World Health Organisation (WHO) criteria:

- *Definite*. Clinical manifestations of an AE, including abnormalities of laboratory parameters occurring during the period of drug administration, which cannot be explained by the presence of existing diseases and the influence of other factors and chemical compounds. Manifestations of adverse reaction regress after drug withdrawal and occur with repeated administration.
- *Probable*. Clinical manifestations of an AE that include changes in laboratory values that are temporally related to the use of the investigational product, that are unlikely to be related to comorbidities or other factors, and that regress with drug withdrawal. The response to rechallenge is unknown.
- *Possible*. Clinical manifestations of an AE that include changes in laboratory values that

## Plan for statistical analysis of efficacy and safety parameters

are temporally related to drug administration but can be explained by the presence of comorbidities or the administration of other drugs and chemical compounds. Information on response to drug withdrawal is unclear.

- *Doubtful*. Clinical manifestations of an AE that include changes in laboratory values that occur in the absence of a clear temporal relationship to drug administration; other factors (drugs, diseases, chemicals) are present that may be responsible for their occurrence.
- *Conditional*. Clinical manifestations of an AE involving abnormalities of laboratory indications categorised as 'adverse reactions' that need further data (for accurate assessment) or these obtained data are currently being analysed.
- *Unclassifiable*. Reports of a suspected adverse reaction cannot be evaluated because there is insufficient or conflicting information.

The occurrence of an adverse event will be considered to be related to the investigational product if the relationship is considered by the investigator as definite, probable, possible.

**Serious adverse event (SAE)** - "Serious" adverse event is defined as any adverse medical event that, regardless of the dose of the medicinal product:

- resulted in death;
- was life-threatening;
- has caused severe or permanent disability or incapacity for work;
- required an inpatient admission (other than a previously planned admission) or causes an extension of the current hospitalization;
- resulted in a congenital anomaly/developmental defect;
- required medical intervention to prevent the above conditions;
- there has been transmission of an infectious agent through a medicinal product.

In addition, a serious adverse event includes any event that does not formally fit the above criteria but is a significant medical event from the investigator's point of view.

"Serious" adverse reaction is a serious adverse event with a causal relationship (possible, probable, or credible) to the use of the investigational product;

All other AEs that do not meet these criteria will be considered as "non-serious".

If a patient develops an AE or SAE, it is mandatory that the appropriate forms are completed for the patient and attached to the patient's CRF. The safety assessment population will be used for all safety analyses.

Early withdrawn patients will be present in the patient list, and summarized by the main reason for withdrawal, and for each treatment group. Missing or omitted data will not be replaced.

Clinical laboratory assessments will be presented with descriptive statistics by trial visit indicating changes from baseline. Laboratory abnormalities outside of normal values will be noted. Lists and summary descriptions of clinically significant haematological laboratory abnormalities will be presented. The feasibility of using a number of statistical methods will be assessed after data collection has been completed, as the nature of the data distribution, sample

### **Plan for statistical analysis of efficacy and safety parameters**

homogeneity, etc. is not known in advance. During the course of the analysis, the list of methods to be used may be modified and supplemented if necessary for the qualitative processing of the data. All deviations from the statistical plan of the survey as well as their causes will be detailed in the statistical report.

Vital signs will also be presented with descriptive statistics showing changes from baseline.

Data harmonisation, if possible, will be done by converting values to commonly used or most common units of measurement in the dataset. In case the units of measurement cannot be harmonised, the data will be presented as tables without further statistical treatment.

Based on the results of the trial, after the final statistical analysis, a conclusion will be made about the efficacy and safety of Mexidol® vs. placebo.

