The  $\chi$ -square test or Fisher's exact test will be used to assess differences in event rates.

The  $\chi$ -square test or Fisher's exact test will also be used to assess differences in patient adherence.

Safety parameters will be tabulated for all patients receiving Investigational product/placebo. Comparisons of safety outcomes between trial groups will be made using the  $\chi$ -square or Fisher's exact test (for qualitative data) and the t-test for data whose distribution follows the law

of normal distribution or its non-parametric analogue (for data whose distribution does not follow the law of normal distribution).

A detailed plan for the statistical analysis of the data will be presented in a separate document to be included in the clinical trial report submitted to the regulatory authority.

Deviations from the statistical analysis plan that occur will be described in the clinical trial report.

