To assess the variability of the effect, the coefficient of variation (CV) value was calculated for all the above change values in the active treatment group:

$$CV = \frac{SD}{M}$$

The following values are obtained:

- 114%
- 167%

of which the maximum of 167% was used to estimate the standard deviation, which for the selected value of change corresponds to the value of  $4.5 * 1.67 = 7.515$ .

For the placebo group, the actual data above were used (-2.0 and -4.7 for mean and standard deviation, respectively).

In order to calculate the sample size, the following assumptions were made:

1. One-sided hypothesis of superior efficacy of Mexidol® over placebo.
2. The mean change in SNAP score in the placebo group is -2.0 points, and the standard deviation for the change is 4.70 points.
3. The mean change in SNAP score in the Mexidol® group is -4.5 points, and the standard deviation for the change is 7.515 points.
4. The modulus of the difference in mean SNAP scores between the Mexidol and placebo groups is 2.5 points
5. The pooled variance estimate (pooled variance) is:

$$SE = \sqrt{\frac{CO_1^2 + CO_2^2}{2}} = \sqrt{\frac{0.12, 0.46}{2}} = 6.27$$

6. The minimum adequate strength is 80% (consequently, the II error is 0.20).
7. The ratio of group volumes is 1:1:1:1.
8. The significance level is 95% (respectively, the I error is 0.05). Since the boundaries of the 95% confidence interval must be two-sided and testing of the superiority hypothesis is one-sided, a one-sided error I of 0.025 will be applied to test the hypothesis, which is equivalent to an error of 0.05 for a two-sided test.
9. 20% drop-out rate during screening.
10. 10% drop out rate during follow-up (based on the above studies).

All calculations were based on the formulae from the book (page 228), where the approximating function for power is given by the following equation

$$1 - \beta = 1 - F(t_{K,\alpha} - \Delta)$$

$$\frac{\sigma\sqrt{2/n}}{\Delta}$$

Where  $\Delta$  - clinically acceptable minimal difference (difference) from placebo and  $Fz = \int_{-\infty}^{z_{\alpha/2}} \text{Normal}(0,1) dz$ , which can also be written by the following expression for n:

$$n = \frac{2\sigma^2 [t_{\alpha/2} + z_{\beta}]^2}{\Delta^2}$$

Calculations were performed using the statistical package PASS 11 (NCSS Inc., USA), which is a validated package that uses formulae directly from the book by Chow et al. cited above.

The results of the calculations are as follows:

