### **9.3. *Applied significance level***

The plan is to apply a significance level of 0.05 and calculate a two-sided 95% confidence interval.

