## 8. Estimation of the required sample size

The sample size calculation is based on the guidelines outlined in Chow S, Shao J, Wang H. Sample Size calculation in Clinical Research. 2nd edition. 2008.

The present trial assumes a 1:1:1 distribution of patients into groups ( $\mu_1 = \mu_2 = \mu_0$ ).

The following input data are used in the calculations:

1. The significance level is 95% (respectively, the I error is 0.05). Since the boundaries of the 95% confidence interval must be two-sided and testing of the superiority hypothesis is one-sided, a one-sided error I of 0.025 will be applied to test the hypothesis, which is equivalent to an error of 0.05 for a two-sided test.
2. Acceptable trial power is at least 80 per cent;
3. The mean change in SNAP-IV score in the placebo group is -2.0 points, and the standard deviation for the change is 4.70 points.
4. The mean change in SNAP-IV score in the Mexidol® group is -4.5 points, and the standard deviation for the change is 7.515 points.
5. The modulus of the difference in mean SNAP-IV scores between the Mexidol and placebo groups is 2.5 points

Thus, based on the calculations based on the data above, the number of patients to complete the trial according to the protocol was at least 100 in each group or a total of at least

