**for categorical data:**

- frequency;
- portion (%).

In addition, calculation of 95% confidence intervals (95% CI, L; 95% CI, U) and range will be used.

The Shapiro-Wilk test will be used to assess the normality of the distribution for indicators with interval type of scale. Pearson's  $\chi^2$  (chi-square) exact test or Fisher's exact test (in case the absolute frequency of a trait is 5 or less) will be used to compare groups on qualitative traits.

To test the null hypothesis of no difference between groups for qualitative features not specified as direct measures of efficacy (secondary endpoints) as well as qualitative measures of safety, testing of the null hypothesis of no difference between groups is planned using the  $\chi^2$  test or Fisher's exact test.

The feasibility of using a number of statistical methods will be assessed after data collection has been completed, as the nature of the data distribution, sample homogeneity, etc.

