## Plan for statistical analysis of efficacy and safety parameters

Table 14. Summary table of the incidence of reported AEs in the group taking Mexidol = placebo by severity with randomization numbers of patients (N=)

Adverse eventcode PT level according to MedDRA version	Mild AE		Medium AE		Moderate AE		Life-threatening AE		Fatal AE		Total		Total R+UR
	R	UR	R	UR	R	UR	R	UR	R	UR	R	UR	
Eyes													
Vascular system													
...													

Table 15. Summary table of the incidence of AEs after taking each investigational product

Adverse eventcode PT level according to MedDRA version	Mexidol N=		Mexidol+placebo N=		Placebo N=		P-value (Statistical criterion)
	n	%	n	%	n	%	
Eyes							
Vascular system							

Table 16. List of all adverse events for each patient

Site number	Randomization number, full name	Demographic data	AE/code, PT according to MedDRA version	AE onset	Severity	Seriousness	Relationship	Actions taken in relation to the patient	Actions taken in relation to the investigational product	Concomitant therapy	Date the AE resolved	Outcome
		Age, y										
		gender										

 A - AE associated with the investigational product; UR - AE unrelated to the investigational product; R+UR - sum of related and unrelated AEs; nm - degree of relationship, where n is the number of AEs; m 1 - definite relationship; m 2 - probable relationship; m 3 - possible relationship; for an example of filling in, see Table 12

Version 1.0 of 27.9.2019

Protocol-specific version for protocol #PHS-ADHD-002-MEX- TAB,  
version 3.0 dated 19.07.2019.

CONFIDENTIAL

page 39 of 42

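### A safety conclusion against placebo is promised, but the only between-arm comparison specified for adverse event rates is a test of no difference, with no interval for the rate difference

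*SAP*

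**What the plan says.** Evaluating safety against placebo, through the frequency, severity and nature of AEs, is a secondary objective in Protocol Section 3.2 and SAP Section 1. SAP Section 10 closes with the commitment that "a conclusion will be made about the efficacy and safety of Mexidol® vs. placebo". No margin or rule for reaching that conclusion is given.

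The between-arm method is a significance test. Protocol Section 9.1 says: "Comparisons of safety outcomes between trial groups will be made using the" chi-square or Fisher test for qualitative data, and the t-test or a non-parametric analogue otherwise. SAP Section 9 says that for secondary qualitative features, "as well as qualitative measures of safety, testing of the null hypothesis of no difference between groups is planned", again by chi-square or Fisher. Fisher's test applies when the absolute frequency of the trait is 5 or less; whether this means the count in one arm or in both together is not stated.

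Table 15 ("Summary table of the incidence of AEs after taking each investigational product") has n and % for each of three arms and one P-value column. Table 21, the equivalent for serious AEs, has n, % and a P-value for Mexidol and placebo only.

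Confidence intervals for a between-arm difference are specified for efficacy. SAP Section 9 adds, after its list of descriptive statistics, that 95% intervals and the range will be used. It does not mention an AE rate difference, and no AE table has a cell for one.

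**The concern.** A test of no difference does not show how large an excess over placebo the data still allow. A conclusion on safety against placebo needs exactly that, for each dose. If most AE rows carry only a P-value, most will be non-significant whether or not the drug raises the rate, and a reader can easily take this as reassurance.

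The stakes are not trivial. SAP Section 2 says that the results go into the registration dossier, and Protocol Section 2.4 says that the drug has not been studied in controlled trials in children. The planned size was set by the efficacy endpoint alone; neither document states power, precision or a margin for safety.

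**Working it through.** **Inputs from the documents.** Protocol Section 9.3: "The plan is to apply a significance level of 0.05 and calculate a two-sided 95% confidence interval". No separate level is given for safety. Protocol Section 9.2 gives 100 completers and 111 randomised per group. The safety population is everyone dosed, so at most 111 per arm.

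**The plan's own sample size.** Protocol Section 9.2: "The modulus of the difference in mean SNAP scores between the Mexidol and placebo groups is 2.5 points". For placebo, "the standard deviation for the change is 4.70 points"; for Mexidol it is 7.515. SAP Section 8: "Acceptable trial power is at least 80 per cent".
- Pooled SD = sqrt((4.70² + 7.515²)/2) = 6.27.
- n = 2 × 6.27² × (1.96 + 0.84)² / 2.5² ≈ 99 by the normal formula. The t-based version gives 99.6, so 100 per group.
- 100/0.9 = 111.1, stated as 111.

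The stated size is reproduced, and it rests on SNAP-IV only.

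**Assumption.** Neither document gives AE rates for children. I take 5% on placebo and 10% on one dose as an illustration.

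**Chance of a non-significant result.** All outcomes of two binomials with n = 111 were enumerated, two-sided 0.05:

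| Test rule | Non-significant, 5% vs 10% |
|---|---|
| Fisher if the smaller arm's count is 5 or less, else uncorrected chi-square | 76.8% |
| Fisher if the combined count is 5 or less, else uncorrected chi-square | 69.9% |
| Always Fisher | 78.4% |
| Always uncorrected chi-square | 69.9% |

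The first two rows are the two readings of the SAP's rule, hence 70% to 77%. For other assumed rates the two readings give 79% and 72% (2% vs 6%), and 44% under both (10% vs 20%).

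If the single P-value in Table 15 is a three-arm chi-square, the figure is about 74% with both doses at 10%, 70% with one dose at 10% and the other at 5%, and 78% with one at 10% and the other at 7.5%. The message is the same whichever comparison is meant.

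**What one such result leaves open.** Suppose 11/111 (9.91%) against 6/111 (5.41%), a difference of 4.50 points.
- Chi-square: the pooled rate is 17/222 = 7.66%, so z = 0.0450 / sqrt(0.0766 × 0.9234 × 2/111) = 1.26 and p = 0.21. Fisher gives p = 0.31.
- Wilson 95% limits: 5.62% to 16.88%, and 2.50% to 11.29%.
- Newcombe lower limit: 4.50 - sqrt((9.91 - 5.62)² + (11.29 - 5.41)²) = -2.8 points.
- Newcombe upper limit: 4.50 + sqrt((16.88 - 9.91)² + (5.41 - 2.50)²) = +12.1 points.

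**Typical precision.** At true rates of 5% and 10% the half-width is 1.96 × sqrt(0.05 × 0.95/111 + 0.10 × 0.90/111) = 6.9 points.

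**Events not seen.** With 0/111, the one-sided 95% upper bound is 1 - 0.05^(1/111) = 2.7%. With 0/222 (both doses pooled) it is 1.3%.

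**The case against.** Neither document says that a non-significant test shows safety. A reader might infer from the test-only comparison that the safety conclusion rests on P-values alone. The documents do not support that. SAP Sections 6 and 10 plan counts of AEs and of patients with AEs, related AEs, events needing discontinuation, severity by organ class, patient listings, and laboratory and vital-sign changes. Table 15 sets n and % for the three arms side by side, from which anyone can work out a difference and its interval. The general line on 95% intervals in SAP Section 9 follows the list for categorical data, so per-arm intervals for AE proportions are a fair reading. All of this stands. What is missing is narrower: a specified interval for the between-arm difference and a place to report it.

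A reader might also infer that the missing interval causes the 70% to 77% miss rate. It does not. That figure comes from 111 per arm, and adding intervals leaves it unchanged; 80% power at these rates would need about 435 per arm.

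Nor do the documents show that Table 15's P-value is a three-arm homogeneity test. The shell does not say, and the continuous safety tests named in SAP Section 6 are two-sample tests. Likewise, the missing column in Table 21 need not mean that the once-daily group is to be left out. The Table 19 shell, titled as a placebo-only severity table, has the three-arm layout with a P-value, so a template slip is possible.

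Finally, SAP Section 10 allows methods to be added during the analysis. That permits the intervals but does not commit to them, and choosing them after seeing the data is weaker.

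**Conclusion.** The point holds as a gap in the specified safety analysis. The plan promises a conclusion against placebo, but its only specified between-arm comparison of AE rates is a test of no difference. That test has limited ability to detect an excess of moderate size and does not report how large an excess remains possible. The relevant size is the undisclosed uncertainty: about ±7 percentage points at assumed rates of 5% and 10%, with an upper limit of 12.1 points in the worked example. The 70% to 77% chance of a non-significant result shows why the test alone is uninformative; it rests on those assumed rates, on 111 dosed children per arm and on the two readings of the Fisher rule. The primary analysis and data collection are not affected. This is a cheap improvement that should be made.

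**What to change.** Keep the chi-square and Fisher tests, since Protocol Section 9.1 prescribes them, and make these additions to SAP Section 10 and Tables 15 and 21:

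- The risk difference with a two-sided 95% interval (for example Newcombe), counted by patients with the event, for twice-daily against placebo and once-daily against placebo, with the pooled doses against placebo as supportive. Cover at least any AE, related AE, serious AE, AE leading to discontinuation, and each organ class.
- The Mexidol+placebo column in Table 21, and a check of the Table 19 shell against its title.
- A label on each P-value saying which arms it compares, and a statement of what count the Fisher rule refers to.
- Exact upper bounds for events not seen.
- A sentence saying that the safety conclusion is drawn from these estimates and intervals, and that a non-significant test is not evidence of no difference.

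The cost is SAP wording and two table shells, plus a correction to Table 19 if its layout proves to be a slip; no new data or patients are needed. The intervals will be many, descriptive and not adjusted for multiplicity, and this should be stated. They will also be wide, so the safety statement becomes more cautious. They do not raise power, and without a margin they do not amount to a formal decision rule.

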## **11. Patient populations to be analysed**

The following groups will be used for the analysis:

1. **Safety population** - will include all patients who have taken at least one dose of the investigational product;

2. **Full analysis set (FAS) population** - will include all randomized patients who have taken at least one dose of the investigational product and who have an assessed response to therapy after 6 weeks of therapy. This will be the main population for efficacy analyses;

3. **Per protocol population (PP)** is a subgroup of the FAS population that will include patients in the absence of significant protocol deviations regarding inclusion/non-inclusion criteria, adherence to therapy, and use of concomitant therapy. This will be an additional population used for efficacy analyses.

Efficacy analyses will be performed on the FAS population as well as on the PP population of all patients who completed the trial according to the protocol in order to validate the results obtained.

The final Clinical Trial Report will include data on all patients included in the trial, including those who dropped out at any time without explanation.

In general, any deviation from the protocol may be accepted only in an urgent case or after obtaining written agreement from the Sponsor and subject to approval by the Ethics Committee. Any deviation from the protocol should be clearly explained in the source documentation and in the eCRF. Classification of protocol deviations will be made by the Sponsor's medical expert before the database lock. Deviations from the protocol will be considered significant in the following cases (the list may be expanded in a subsequent evaluation of protocol deviations):

- skip of visit 4;
- violation of inclusion / non-inclusion criteria;
- violation of the exclusion criteria;
- taking the investigational product/placebo <80% or >120% of the total number of tablets prescribed;
- administration of prohibited drugs.

